## 2.0 Background

Despite substantial advances in screening, monitoring, therapeutics and management, CMV infection remains a significant problem in kidney transplantation and CMV is still considered by clinicians to be the most important post-transplant infection. Although universal prophylaxis with potent antiviral therapy has significantly reduced the risk of early CMV infection and disease ( $\leq 6$  months), late onset CMV ( $> 6$  months post-transplant) is still quite common and can be difficult to clinically manage, particularly in high-risk patients, including those receiving rabbit antithymocyte globulin (rATG) induction and those that are sero mismatched (D+/R-). A recent systematic review demonstrated that with antiviral prophylaxis, early CMV infection occurred in only 6% (95% CI 1 to 31%) of kidney transplant recipients, while late infection occurred in more than one in six patients (17%, 95% CI 2 to 29%). The results of the IMPACT study, a randomized controlled trial comparing 100-days to 200-days of oral valganciclovir therapy in D+/R- patients highlights the continued issue of late CMV infection. Although patients randomized to the 200-days of therapy had a significant reduction in CMV disease, rates were still quite high. The 12-month incidence of CMV disease was 16.1% in these patients, despite receiving more than 6-months of valganciclovir prophylaxis.

Valganciclovir antiviral prophylaxis is highly effective at preventing CMV infection, but it has numerous limitations. Of particular concern is the high rates of cytopenias; most notably, leukopenia and neutropenia. This often leads to a clinical conundrum, whereby it is unclear if the low WBC count is due to valganciclovir therapy itself, a breakthrough CMV infection, or mycophenolate therapy. Oftentimes, this clinical dilemma causes multiple additional laboratory interrogations, reductions in full dose valganciclovir and/or mycophenolate therapies, and in severe cases, the administration of filgrastim (Neupogen®, G-CSF). In studies using valganciclovir for CMV prevention, the reported the incidence of post-kidney transplant leukopenia is 20 to 40% and neutropenia is upwards of 10% at 30%.

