### 4.0 Study Endpoints

#### Safety Measures

1. Leukopenia with an accompanying dose reduction (Primary Outcome) – Defined as a total WBC count of  $< 3,000$  cells/mm^3 with a reduction in the total daily dose of mycophenolate below 1500mg per day or valganciclovir below 900mg daily (adjusted for renal function). This will be assessed as a dichotomous outcome (yes/no) per patient as well as a rate (number of unique leukopenia events per patient-year). Events will be considered unique once the WBC count recovers to normal range on two consecutive measures. The length of time a patient has leukopenia, and the severity of leukopenia (nadir WBC) will also be assessed. This endpoint will be measured at 3-, 6-, and 12-months post-transplant.

2. Neutropenia (Secondary Outcome) – Defined as an absolute neutrophil count of  $<1,000$  cells/mm^3. This will be assessed as a dichotomous outcome (yes/no) per patient as well as a rate (number of unique neutropenic events per patient-year). Events will be considered unique once the neutrophil count recovers to normal range on two consecutive measures while not receiving G-CSF therapy. The length of time a patient has neutropenia, and the severity of leukopenia (nadir WBC) will also be assessed. This endpoint will be measures at 3-, 6-, and 12-months post-transplant.
3. Mycophenolate mofetil dose reduction (Secondary Outcome) – Defined as a reduction in dose of  $<1,500$  mg per day ( $<750$  mg PO BID). This will be assessed as a dichotomous outcome (yes/no) per patient as well as a rate (number of unique mycophenolate dose reduction events per patient-year). Events will be considered unique once the mycophenolate dose is returned to full dose for at least one week. The length of time a patient has their mycophenolate dose  $<1,500$  mg per day and the severity of mycophenolate dose reduction (nadir dose) will also be assessed. This endpoint will be measures at 3-, 6-, and 12-months post-transplant.

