The incidence of clinically significant leukopenia (WBC <3K AND dose reduction in MMF) is difficult to assess in the maribavir arm, as this specific issue is not reported in the published data. However, there are several studies that can be used to estimate this incidence for power/sample size purposes. In a study conducted in liver transplant patients, known to be at higher risk for cytopenias than kidney recipients, the incidence of neutropenia was 6% in the maribavir arm (Winston DJ et al Am J Transplant 2012;12:3021-30.). In a phase III prophylaxis study in allogeneic stem-cell transplants, who are very high risk for cytopenias, the incidence of neutropenia was similar between the maribavir, and placebo arms and the average WBC count was 4.2K in the placebo arm and 4.4K in the maribavir arm (Papanicolaou GA et al. Clin Inf Diseases 2019;68:1255-64.). Thus, maribavir does not appear to induce or worsen leukopenia and a 5% incidence is a reasonable expectation in the maribavir treatment arm for estimating sample size and power.

To meet at least 80% power, given an incident rate of 33 to 35% in the valganciclovir arm and 5 to 6% in the maribavir arm, 32 patients in each arm is required, assuming two independent samples, a two sided  $\alpha=0.05$ , and using the chi square test. This sample-size will be inflated to 35 patients per arm to address an expected dropout/lost to follow-up rate of 3-5% in each arm. Thus, 70 total patients, 35 in each arm, will provide adequate power to assess the primary aim of this study. SAS 9.4 (SAS Institute, Cary, NC) was utilized to conduct sample-size estimations (Proc Power).

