## 12.0 Data Management

Data capture will be accomplished using an electronic extraction and a study coordinator for manual chart abstraction. Data will be collected in a comprehensive longitudinal manner by review of the patient's electronic and paper medical records. Data collection will include all baseline donor/recipient demographics and transplant characteristics as well as longitudinal collection of medications, laboratory data and clinical events during

the post-transplant timeframe. The Research Electronic Data Capture (REDCap) system will be used for data management. REDCap is a secure, web-based application designed exclusively to support data capture for research studies. REDCap provides: 1) an intuitive interface for data entry (with data validation); 2) audit trails for tracking data manipulation and export procedures; 3) automated export procedures for seamless data downloads to common statistical packages (SPSS, SAS, Stata, R); 4) procedures for importing data from external sources; and 5) advanced features, such as branching logic and calculated fields. The REDCap project (<http://project-redcap.org/>) was initiated at Vanderbilt University and includes more than 70 active institutional partners from CTSA, GCRC, RCMC funded institutions, including MUSC, and others through a collaborative international consortium.

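### The leukopenia event rule lacks the off-G-CSF condition that the neutropenia rule has, so one course can be counted as two events; neutropenia severity is graded by nadir WBC instead of nadir ANC

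*Combined protocol and SAP*

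**What the plan says.** Section 4.0 (Safety Measures) defines leukopenia with dose reduction as item 1, the primary outcome, and neutropenia as item 2, a secondary outcome.

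- **Forms of item 1.** It is assessed as yes/no per patient, "as well as a rate (number of unique leukopenia events per patient-year"), and descriptively: "The length of time a patient has leukopenia, and the severity of leukopenia (nadir WBC) will also be assessed".
- **Event separation, item 1.** "Events will be considered unique once the WBC count recovers to normal range on two consecutive measures". G-CSF is not mentioned.
- **Event separation, item 2.** A neutropenia event is closed when the neutrophil count "recovers to normal range on two consecutive measures while not receiving G-CSF therapy".
- **Severity, item 2.** "The length of time a patient has neutropenia, and the severity of leukopenia (nadir WBC) will also be assessed". Nadir ANC is not named anywhere in the document.

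Section 2.0 (Background) describes the response to low counts as including, "in severe cases, the administration of filgrastim". Section 12.0 provides for "longitudinal collection of medications, laboratory data and clinical events". Neither that section nor the follow-up table in Section 10.0 names G-CSF as a data element.

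**The concern.** Item 2 treats a normal neutrophil count on G-CSF as not yet a recovery. Neutrophils are part of total WBC, so the same reasoning applies to item 1, yet item 1 accepts such counts. Two adjacent endpoints can therefore score one clinical course differently, and the looser rule belongs to the primary outcome.

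What is at stake is the event-rate form of the primary outcome and, depending on how duration is computed, the time spent with leukopenia. The trial is open-label and cytopenias are managed by usual care, so nothing in the design makes G-CSF use equal between arms. If the counting rule is settled only at analysis, the choice of which episodes count will be made with treatment known.

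The severity wording in item 2 is a separate matter. Items 3, 4 and 5 each grade severity by the nadir of their own variable. Item 2 instead repeats item 1's descriptor, so the stated measure is not about neutrophils.

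**Working it through.** **1. What the rule does and does not enter.** The plan's sample size is for the yes/no outcome, with two-sided alpha 0.05, at least 80% power "and using the chi square test". For the tabulated scenario of 33% vs 6% (total 64, so 32 per arm), the pooled normal approximation without continuity correction is

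n = [1.96·√(2·p̄·q̄) + 0.8416·√(p₁q₁ + p₂q₂)]² / (p₁ − p₂)², with p̄ = 0.195

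= [1.96·√0.31395 + 0.8416·√0.2775]² / 0.27² = 2.376 / 0.0729 = 32.6, so 33 per arm.

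The plan states 32. At 32 per arm the same approximation gives power 0.792 against the tabulated 0.809. The plan's figure is reproduced closely, and no event-separation rule enters it. A patient with one event or two is a yes either way.

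**2. One constructed patient, both rules.** All values are assumed: weekly counts, lower limit of normal 4.0 K, G-CSF on days 14 and 21. It is also assumed that a dose reduction qualifies both dips, and that duration runs from the first low count to the first of the two normal counts.

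| Day | 0 | 7 | 14 | 21 | 28 | 35 | 42 | 49 | 56 |
|---|---|---|---|---|---|---|---|---|---|
| WBC (K) | 2.4 | 2.1 | 5.2 | 5.0 | 2.6 | 2.5 | 3.4 | 4.6 | 4.8 |
| G-CSF | no | no | yes | yes | no | no | no | no | no |

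- Item 1 as written: days 14 and 21 close the first event. Two events, of 14 days (0 to 14) and 21 days (28 to 49), 35 days in total.
- With item 2's off-G-CSF condition: days 14 and 21 do not count. One event of 49 days (0 to 49).

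**3. Effect on the event rate.** Inputs from the plan are 35 per arm and incidences of 35% and 5%. Assumed are one year of follow-up for all and one true event per affected patient.

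- Valganciclovir: 0.35 × 35 = 12.25 events. Maribavir: 0.05 × 35 = 1.75. Rate ratio 1.75 / 12.25 = 0.143.
- Let f be the share of events given G-CSF, and s the share of those that relapse after two normal on-treatment counts. The recorded count becomes 12.25 × (1 + f·s). Neither f nor s is in the documents.

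| f | s | Valganciclovir events, splitting in that arm only | Change | Rate ratio |
|---|---|---|---|---|
| 10% | 50% | 12.9 | +5% | 0.136 |
| 25% | 50% | 13.8 | +12.5% | 0.127 |
| 50% | 100% | 18.4 | +50% | 0.095 |

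With the same f and s in both arms, (1 + f·s) cancels and the ratio stays at 0.143.

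**4. Severity.** Take two illustrative patients, both neutropenic under item 2 (ANC below 1,000): A with ANC 300 and WBC 3,100, B with ANC 900 and WBC 2,000. By nadir WBC, A ranks milder; by nadir ANC, A ranks more severe. A is not even below item 1's threshold of 3,000, so a leukopenia severity says nothing useful about A's neutropenia.

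**The case against.** The strongest reply is that nothing the trial is powered on moves. Section 10.0 powers the study on the incidence of leukopenia with dose reduction, and Statistical Methods names chi-square or Fisher tests for incidence but no method specific to events per patient-year. That stands: a reader might infer that the primary comparison is compromised, and the documents do not support this.

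Second, splitting is conditional. It needs G-CSF, two consecutive normal counts on it, and a later relapse. Item 1 also requires a dose reduction, and the plan does not say whether a reduction still in force qualifies a second event; item 3 keeps an unrestored mycophenolate reduction as one event. This stands too, so the rule can split a course but does not necessarily do so.

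Third, shortening is an inference. The plan does not say how the length of leukopenia is computed. If it means days below 3,000, the recovery rule has no bearing on it.

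Fourth, a reader might infer a bias in favour of maribavir. The documents give no G-CSF use by arm. The Background's neutropenia figures (15-18% on valganciclovir, 4-5% on maribavir) make unequal use plausible, but they come from treatment studies and are not G-CSF rates. If use were higher on valganciclovir, the event rate would shift in favour of maribavir, while any shortening of duration would favour valganciclovir.

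Fifth, it would go too far to say that neutropenia depth cannot be known. ANC is needed to apply the definition, so nadir ANC can be derived. The wording looks carried over from item 1. It is still the stated measure, and nothing elsewhere corrects it.

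**Conclusion.** Both textual points hold, and no other section repairs them. Item 1's rule can count one G-CSF-supported course as two leukopenia events, and can shorten its duration if the same rule ends the episode. The effect is confined to the events-per-patient-year form and possibly the duration form. The yes/no outcome, its power, the sample size and nadir WBC are unaffected.

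The size cannot be fixed from the documents. Under the assumptions shown, with splitting on valganciclovir only, recorded events in that arm rise from 12.25 to between 12.9 and 18.4. The upper figure requires G-CSF in half of events and relapse in all of those, so it marks an extreme. A biased rate ratio requires G-CSF use or relapse to differ by arm.

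The severity measure in item 2 names the wrong variable, which is certain from the text and simple to correct. The whole point is worth settling before episodes are classified, but it is no threat to the main result.

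**What to change.** 1. In item 1, add item 2's condition: events are separated only by two consecutive normal WBC counts obtained off G-CSF. State that the same rule ends the episode when duration is computed.
2. In item 2, replace the severity descriptor with severity of neutropenia, measured by nadir ANC.
3. Name G-CSF start and stop dates among the medication data, and report G-CSF use by arm.

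The cost is the wording of two definitions and one named data element. Medications and laboratory values are already abstracted, and item 2 cannot be scored without G-CSF status in any case. No tests, visits, treatment decisions or sample size change.

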### 3.0 Intervention

Patients will be randomized to receive either maribavir 400mg PO BID or valganciclovir 900mg daily (standard of care dose, adjusted for renal function) for CMV prophylaxis for 3 to 6 months post-transplant. Those that are CMV serostatus D+/R- will receive 6 months of antiviral therapy; all others will receive 3-months of therapy. The current gold-standard therapy is valganciclovir for 3- to 6-months of therapy. Those randomized to maribavir will also receive 1-month of acyclovir 400mg PO BID for HSV prophylaxis (standard of care dose). Beyond these interventions, all follow-up care and laboratory monitoring will be conducted as per usual care protocols. All immunosuppression will be given and dosed as per usual care protocols. There will be no additional visits or laboratory measurements as part of this study.

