4. Valganciclovir dose reduction (Secondary Outcome) – Defined as a reduction in dose of  $<900$ mg per day (adjusted for renal function. This will be assessed as a dichotomous outcome (yes/no) per patient as well as a rate (number of unique valganciclovir dose reduction events per patient-year). Events will be considered unique once the valganciclovir dose is returned to full dose for at least one week. The length of time a patient has their valganciclovir dose reduced and the severity of dose reduction (nadir dose) will also be assessed. This endpoint will be measures at 3-, 6-, and 12-months post-transplant.
5. CMV prophylaxis drug dose adjustment or discontinuation (Secondary Outcome) – Defined as a reduction in dose, holding or discontinuation of the maribavir or valganciclovir therapy. This will be assessed as a dichotomous outcome (yes/no) per patient as well as a rate (number of unique dose adjustment events per patient-year). Events will be considered unique once the CMV prophylaxis drug dose is returned to full dose for at least one week. The length of time a patient has their CMV prophylaxis drug dose reduced or held and the severity of dose reduction (nadir dose) will also be assessed. This endpoint will be measures at 3- and 6-months post-transplant.
6. Acute Rejection (Secondary Outcome) - defined as a renal allograft biopsy demonstrating at least grade 1A rejection by Banff criteria. We will also record and assess all borderline acute rejections and antibody mediated rejections using the most current Banff classification system. All patients will be required to have biopsy confirmation of rejection episodes, as per usual care and the MUSC clinical protocol. It is standard care that all kidney allograft biopsies performed for transplant recipients occur at the transplant center (study institution). Biopsies will be read by the local pathologist, as usual care. The study coordinator capturing clinical event data will review the medical record to determine the timing, severity, treatment regimen and reversibility of each acute rejection episode for all patients in the study.
7. Hospitalizations (Secondary Outcome) – Defined as any admission to a hospital with at least one overnight stay. All-cause hospitalization will be assessed for this study. Hospitalizations due to CMV and other infections will be sub-analyzed as well.

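### The antiviral dose-change endpoint (item 5) has no renal-function qualifier, so as written routine renal adjustments count as events in the valganciclovir arm only

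*Combined protocol and SAP*

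**What the plan says.** All references are to the combined protocol and SAP.

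- **Item 5 (Section 4.0, Safety Measures).** The event is "Defined as a reduction in dose, holding or discontinuation of the maribavir or valganciclovir therapy". It is analysed as yes/no per patient and as a rate per patient-year, with duration and nadir dose. On repeat events: "Events will be considered unique once the CMV prophylaxis drug dose is returned to full dose for at least one week". On timing: "This endpoint will be measures at 3- and 6-months post-transplant".
- **Items 1 and 4 (same section).** The primary endpoint refers to "valganciclovir below 900mg daily (adjusted for renal function"), and item 4 sets its threshold in "mg per day (adjusted for renal function"). Both carry the renal qualifier that item 5 lacks.
- **Regimens (Section 3.0, repeated in Section 10.0).** Patients receive "maribavir 400mg PO BID or valganciclovir 900mg daily (standard of care dose, adjusted for renal function"). The adjustment is attached to valganciclovir; maribavir is stated as one fixed dose.
- **Duration (Section 3.0).** D+/R- patients have a 6-month course; "all others will receive 3-months of therapy". Section 5.0 admits rATG recipients of any serostatus, so 3-month courses will occur.
- **Analysis (Section 10.0, Statistical Methods).** Interruption of prophylaxis dosing is among the key outcomes to be compared by chi-square or Fisher's exact test.

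**The concern.** Item 5 is the only antiviral dose-change endpoint that patients in both arms can meet, since item 4 applies to valganciclovir alone. Readers will naturally use it to compare how well the two drugs are tolerated.

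For that purpose an event should mean the same thing in each arm. Here a valganciclovir patient whose dose is lowered because renal function changed meets the definition with no tolerability problem, and the plan gives maribavir patients no corresponding route to an event. Two equally tolerated drugs could show a significant difference.

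The 6-month reading raises a second, smaller question. By then every patient on a 3-month course should have stopped as planned, and item 5 does not say whether that is a discontinuation.

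**Working it through.** The documents state no rate, power or sample size for item 5, so there is no figure of the plan's to reproduce. The text settles whether the gap exists; the arithmetic only illustrates its possible size.

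**1. Comparing the definitions**

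| | Renal qualifier | Arms that can meet it | Planned completion addressed |
|---|---|---|---|
| Item 1, valganciclovir limb | yes | valganciclovir | not applicable (dose threshold) |
| Item 4 | yes | valganciclovir | no |
| Item 5 | no | both | no |

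Item 5 does not say what a reduction is measured from, nor whether full dose in the repeat-event rule means the unadjusted dose or the dose for current renal function. The rate, duration and nadir are therefore affected as well as the yes/no result. A patient who stays on a renally adjusted dose might never return to full dose, which lengthens the recorded event and prevents a later one from counting as new.

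**2. Size of the renal effect**

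Inputs from the plan: 35 per arm (Section 6.0) and the chi-square test (Statistical Methods). The two-sided 0.05 level is stated for the sample-size calculation and assumed here for item 5. Also assumed: a non-renal event rate q equal in both arms, and a proportion r of valganciclovir patients with a renal adjustment, independent of non-renal events.

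Rates: maribavir = q; valganciclovir = 1 − (1 − q)(1 − r). With q = 0.10 and r = 0.20, this is 1 − 0.90 × 0.80 = 0.28.

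Rejection probability: sum Bin(a; 35, p_V) × Bin(b; 35, p_M) over all pairs (a, b) with |a − b|/35 ÷ √(2p̄(1 − p̄)/35) > 1.96, where p̄ = (a + b)/70.

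| r (assumed) | Valganciclovir vs maribavir, q = 10% | Pearson, q = 10% | Fisher, q = 10% | Pearson, q = 5% | Pearson, q = 20% |
|---|---|---|---|---|---|
| 0 | 10% vs 10% | 0.057 | 0.013 | 0.036 | 0.049 |
| 10% | 19% vs 10% | 0.191 | 0.106 | 0.288 | 0.117 |
| 20% | 28% vs 10% | 0.492 | 0.381 | 0.669 | 0.318 |
| 30% | 37% vs 10% | 0.783 | 0.700 | 0.905 | 0.592 |
| 40% | 46% vs 10% | 0.942 | 0.906 | 0.984 | 0.819 |

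The direction is the same for either test and any q shown; the size depends on r.

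**3. Planned completion at 6 months**

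Assume unplanned changes in 35% (valganciclovir) and 5% (maribavir), and a fraction f of each arm on 3-month courses, all counted as events. The rates are then f + (1 − f) × 0.35 and f + (1 − f) × 0.05, and the difference is 0.30 × (1 − f).

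| f (assumed) | 6-month rates | Difference | Exact Pearson power |
|---|---|---|---|
| 0 (completers not counted) | 35% vs 5% | 30 points | 0.93 |
| 30% | 54.5% vs 33.5% | 21 points | 0.41 |
| 50% | 67.5% vs 52.5% | 15 points | 0.24 |
| 70% | 80.5% vs 71.5% | 9 points | 0.14 |
| 90% | 93.5% vs 90.5% | 3 points | 0.08 |

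Both arms rise and the contrast shrinks. This is dilution, unlike the one-sided effect in step 2.

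**The case against.** **The renally adjusted dose is the assigned dose.** The regimen is "valganciclovir 900mg daily (standard of care dose, adjusted for renal function"), so a renal change can be read as following the assignment rather than departing from it. Item 10 also points to an appendix with the usual-care CMV protocol, which is not in the text available here. This reading is fair and probably close to the intent. But items 1 and 4 spell the qualifier out, so its absence from the next item, whose title speaks of dose adjustment, can equally be taken as deliberate. Chart abstraction in an open-label trial should not rest on an unwritten rule.

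**An all-cause count is legitimate.** Item 4 is already renally qualified, and item 5 could measure total dosing burden. On that reading a renal difference is a real difference between regimens. This stands, and is why the all-cause count should be kept, but labelled as burden and not as tolerability.

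**Planned completion.** A reader might infer that every 3-month completer becomes a discontinuation at 6 months. The documents do not establish this. Item 10 refers to the scheduled end both as completion and as discontinuation; Statistical Methods speaks of interruption; and item 5 is read only at 3 and 6 months, the two course lengths, which suggests an on-treatment measure. The text is ambiguous.

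**Importance.** A reader might also infer that item 5 is the only dose-change endpoint common to both arms. It is not: item 3 (mycophenolate reduction) applies to both and has neither problem. Item 5 is unique only among the antiviral dose measures, and it is one of many secondary outcomes in a trial that calls itself small and exploratory.

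**Conclusion.** The renal point holds. As written, item 5 can count protocol-directed renal changes as events in the valganciclovir arm alone, so as a tolerability comparison it is biased against valganciclovir. With an assumed 10% non-renal rate in both arms, the chance of a significant difference rises from about 6% to 19%, 49%, 78% or 94% as the assumed renal-adjustment rate goes from none to 10%, 20%, 30% or 40%. These are illustrations, not predictions: the documents give neither rate, and the calculation assumes independence and that every renal adjustment is counted.

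Planned completion is a secondary ambiguity. If completers were counted, the 6-month difference would shrink in proportion to the share on 3-month courses, which the documents do not give. A systematic bias towards one arm should not be inferred from it, although no stratification by serostatus is described, so a chance imbalance in course length would carry through.

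The primary endpoint carries its own renal qualifier, and the sample size does not depend on item 5; neither is affected. The wording should be corrected because the plan lists this outcome as key and the correction is cheap.

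**What to change.** Amend item 5 and the matching line in Statistical Methods:

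1. Define the event as a reduction, hold or discontinuation before the patient's assigned 3- or 6-month end of prophylaxis, excluding planned completion and excluding changes made only for renal function.
2. In the repeat-event rule, define full dose as the assigned dose for current renal function, consistent with items 1 and 4.
3. For the rate, count person-time only to the assigned end date. For the yes/no result, restricting the window is enough; censoring does not suit an outcome tested by chi-square or Fisher's exact test.
4. Report renal adjustments, and the all-cause count, separately by arm.

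The cost is protocol wording plus one reason-for-change field in chart abstraction; antiviral doses are already collected (Section 10.0, assessment table, footnote 3). The drawback is that assigning a reason takes some judgement by staff who know the treatment arm. Reporting the all-cause count alongside limits that risk. No dose, treatment duration, visit or sample size changes.
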